8.2 Subgroup Definition and Parameterization

Not applicable.

9 General Specifications for Data Analyses

The results of this study will be reported using summary tables, figures, and data listings, as appropriate. All data will be summarized by study intervention and/or scheduled time point, as applicable.

Listings

In the individual participant data listing all individual data will be listed as measured. Repeated and unscheduled measurements will be included in the listings. All listings will be sorted by subject ID and nominal time point, if not stated otherwise.

Tables and Descriptive Statistics

All safety data will be summarized overall by nominal time point, as appropriate. All PK data will be summarized by study intervention and nominal time point. Repeated and unscheduled measurements included in the listings will not be used for statistical analyses or summaries, unless the repeated measurement was performed due to unreliable values/technical reasons, e.g., clotted samples.

Unless otherwise specified, continuous variables will be summarized using descriptive statistics, i.e. the number of participants with non-missing values (n), the number of participants with missing values (nmiss), mean, standard deviation, median, 25th percentile (Q1) and 75th percentile (Q3), minimum, and maximum. If there are no missing values the number of participants with missing values should be indicated by a 0. Mean, Median, Q1, Q3, Min, Max will have the same precision as the SDTM data (decimal places). SD will be presented with one decimal place more than the mean.

Qualitative variables will be summarized by frequency counts and percentages. Unless otherwise stated the calculation of proportions will be based on the number of participants of the analysis set of interest that received the respective study intervention for AE and PK tables and for all other evaluations the analysis set of interest [N]. Therefore, counts of missing observations will be included in the denominator and presented as a separate category.

Study day 1 for this study is defined as the start date of study intervention.

The following labels will be used for the study interventions in safety and PK tables and listings, if not stated otherwise:

COC:	0.03 mg/0.5 mg EE/NET on Day 1
Evobrutinib:	45 mg Evobrutinib twice daily on Days 4 to Day 14
COC+Evobrutinib	0.03 mg/0.5 mg EE/NET on Day 15 plus 45 mg Evobrutinib twice daily on Day 15 to Day 17

All statistical analyses will be performed using SAS® Software version 9.2 or higher.

9.1 Definition of Baseline and Change from Baseline

If not otherwise specified, 'baseline' refers to the last scheduled measurement before administration of study intervention.

However, if a participant is missing the baseline collection, the previous non-missing evaluation could become the baseline value (e.g. from Screening). If no baseline or previous to baseline evaluations exist, then the baseline value will be treated as missing.

Absolute changes from baseline are defined as

$$\text{absolute change} = \text{visit value} - \text{baseline value}$$

9.2 Study Day / Study Intervention Day

Day 1 is the day of start of study intervention, the day before is Day -1 (no Day 0 is defined). Study day is defined relative to Day 1.

9.3 Definition of Duration and ‘Time Since’ Variables

The following definitions and calculations of duration, as applicable, will be applied:

- Duration of AE (in days hh:mm) = end date and time - start date and time of the AE, if missing time for either the beginning or end then = end date – start date + 1; in case of multiple records for the same AE, the duration will be calculated over all these records
- Days hh:mm from dosing (onset post administration) = start date and time of the event - date and time of last dose administration of COC or evobrutinib (calculated for each intervention, for TEAEs), if missing time for either the dosing or event then days hh:mm from dosing = event start date – date of dose administration + 1
- Relative (Rel.) Day in study of AE = start date of the event – date of first admin + 1 (for AEs on or after the day of dosing)
- Rel. Day in study of AE = start date of the event – date of first admin (for events before the day of dosing of the study only)

9.4 Imputation of Missing Data

In this Phase I PK study, missing observations will be assumed to be missing completely at random (MCAR). No action will be taken to handle missing data. A participant who withdraws prior to the last planned observation in a study period will be included in the analyses up to the time of discontinuation.

10 Study Participants

The subsections in this section include specifications for reporting participant disposition and study intervention/study discontinuations. Additionally, procedures for reporting protocol deviations are provided.

10.1 Disposition of Participants and Discontinuations

The following will be presented in a summary table:

- Total number of participants screened (i.e., participants who gave informed consent)
- Number of screened participants who discontinued from the study prior to first dosing overall and grouped by the main reason for discontinuation:
 - Participant did not meet all eligibility criteria
 - Withdraw consent
 - Other (COVID-19-related and COVID-19-non-related)
- Number of treated participants
- Number and percentage of treated participants who completed study

- Number and percentage of treated participants who discontinued the study or study intervention, with the primary reason of discontinuation:
 - Adverse event
 - Lost to follow-up
 - Protocol non-compliance
 - Death
 - Withdrew consent
 - Other (COVID-19-related and COVID-19-non-related)

The number and percentage of participants will be presented by part, group of study intervention and total, where applicable. Percentages will be presented with respect to the number of treated participants, where applicable.

A listing of discontinued participants will be provided.

A listing of participants affected by the COVID-19 related study disruption by unique participant identifier will also be provided.

10.2 Protocol Deviations / Exclusion from Analysis Sets

10.2.1 Important Protocol Deviations

Listings of important protocol deviations will be provided including the date and relative day in relation to dosing in the relevant period. A distinction will be made between important protocol deviations due to COVID-19 versus not due to COVID-19. The respective important protocol deviations will be flagged accordingly.

Important protocol deviations or important events that might influence PK include, but may not be limited to the following:

- Adverse events, diarrhea etc. (these instances will be discussed on a case-by case basis)
- Vomiting after administration following oral dosing (these instances will be discussed in alignment with applicable regulatory guidelines on a case-by-case basis)
- Sample processing errors that may lead to inaccurate bioanalytical results
- Inaccurate dosing or dosing errors (e.g., dose administration delayed, dose change or missed doses)
- Predose or trough sample collected after the actual dosing
- Non-compliance with food and drink requirements (e.g., non-fasted, incomplete meal consumption, caffeine intake)
- Concomitant medication, vitamins, dietary or herbal supplements

Should one or more of these events be available at the Data Review Meeting, its implication for PK evaluation will be discussed and agreed amongst relevant study team members (e.g., Sponsor Clinical Pharmacology/Biostatistics/Clinical Pharmacokinetics & Pharmacodynamics team representative). Appropriate action will be taken such as flagging individual values to be excluded from analysis.

10.2.2 Reasons Leading to the Exclusion from an Analysis Set

If participants are excluded from the PK Analysis Set, the reasons for exclusion will be listed.

Reasons for excluding individual PK concentrations will also be listed separately and flagged in the main listing.

11 Demographics and Other Baseline Characteristics

Demographics and baseline characteristics will be presented for the SAF.

11.1 Demographics

Descriptive statistics will be presented for age, height, weight, and BMI. Frequency counts and percentages will be presented for sex, race, and ethnicity. The summary will be performed overall.

BMI (kg/m^2) will be derived (i.e., not taken directly from the database) according to the following formula:

$$\text{BMI } [\text{kg}/\text{m}^2] = \frac{\text{weight } [\text{kg}]}{\text{height}^2 [\text{cm}^2]} \times 10000$$

11.2 Medical History

Medical history will be coded using the MedDRA, most current version at time of data base lock, and listed.

The medical history will be listed by participant including PT as event category and SOC body term as Body System category.

11.3 Other Baseline Characteristics

Other baseline measurements, such as virus screen, alcohol and drugs of abuse screen, pregnancy test in women, nicotine, and alcohol consumption, will be listed.

Baseline characteristics with respect to vital signs, physical examinations, and hematology/biochemistry will be part of Section 15 (Safety Evaluation).

12 Previous or Concomitant Therapies/Procedures

Medications will be presented for the Safety Analysis Set.

Previous medications are defined as any medication discontinued prior to the administration of study intervention. Concomitant medications are defined as any medication taken during the course of the study, with a starting date greater than or equal to the administration of study intervention, or with a starting date prior to the administration of study intervention and ongoing at the time of the administration of study intervention.

The World Health Organization Drug dictionary most current version at time of database lock, will be used for coding of prior and concomitant medications and they will be described using PT as applicable.

Previous and concomitant medications will be listed. Concomitant procedures, if any, will also be listed.

13 Study Intervention: Compliance and Exposure

The dosing of each participant is monitored by the study nurse or investigator. A listing of date and time of each drug administration and each blood sampling, including time deviations as well as measured plasma concentrations, will be provided sorted by participant. Information on meal intake will be listed by participant, if provided.

14 Efficacy Analyses

Not applicable.

15 Safety Analyses

This section includes specifications for summarizing safety endpoints that are common across clinical studies such as adverse events, laboratory tests and vital signs.

All safety analyses will be performed for the Safety Analysis Set and will be presented by nominal timepoint, as appropriate.

Safety analyses will be done according to the as-treated principle.

15.1 Adverse Events

All AEs recorded during the study will be coded with the MedDRA, latest version at time of database lock, and assigned to a SOC and a PT.

TEAEs are those events with onset dates on or after the first administration of study intervention on Day 1. Any AE occurring before the administration of study intervention on Day 1 and resolved before administration of study intervention or not worsening after administration of study intervention on Day 1 will be included in the AE listings but will not be included in the summary tables (unless otherwise stated). These will be referred to as “pre-treatment” AEs.

In case AE-related dates are partial, the available information will be used in a conservative approach to determine whether the AE is treatment-emergent.

All analyses described in Section 15.1 will be based on TEAEs if not otherwise specified. The AE listings will include all AEs (whether treatment-emergent or not). AEs outside the on-treatment period will be flagged in the listings.

Unless otherwise specified, TEAEs will be summarized, by number and percentage of participants with the TEAE in the category of interest, as well as the number of events, in total by primary SOC and PT in alphabetical order for SOC and decreasing overall frequency for PT.

If an event was reported more than once due to change in intensity and change in relationship, the worst severity and the worst relationship to study intervention will be tabulated.

Each participant will be counted only once within each SOC or PT.

15.1.1 All Adverse Events

TEAEs and participants experiencing TEAEs will be summarized by study intervention and overall with:

- The number and percentage of participants with any TEAE, any related TEAE, any COC-related TEAE, any evobrutinib-related TEAE, any serious TEAE, any related serious TEAE, any COC-related serious TEAE, any evobrutinib-related serious TEAE any severe TEAE, any related severe TEAE, any COC-related severe TEAE, any evobrutinib-related severe TEAE, any AESI, any TEAE leading to death, any related TEAE leading to death, any COC-related

TEAE leading to death, any evobrutinib-related TEAE leading to death, any TEAE leading to study discontinuation

- The number and percentage of participants with at least one TEAE and the number of events by SOC and PT.
- The number and percentage of participants with TEAEs excluding SAEs and the number of events, with frequency $\geq 5\%$ in any study intervention arm by SOC and PT
- The number and percentage of participants with at least one TEAE and the number of events by severity, SOC, and PT
- The number and percentage of participants with at least one related TEAE, evobrutinib-related TEAE, COC-related TEAE and the number of events by SOC and PT
- The number and percentage of participants with at least one AESI recorded and the number of events by SOC and PT.

Unless otherwise stated, AEs will be displayed with SOC terms sorted alphabetically and PTs within each SOC term sorted in descending overall frequency.

For determining incidence counts, within each level of TEAE term, if a participant experiences more than one occurrence, the participant will only be counted once for that TEAE.

AEs related to any study intervention are those events with relationship missing, unknown or yes.

In case a participant had events with missing and non-missing severity, the maximum non-missing severity will be displayed.

15.1.2 Adverse Events Leading to Discontinuation of Study Intervention

A listing of TEAEs leading to discontinuation of study intervention, or discontinuation of study, if any, will be provided.

The frequency (number and percentage) of participants with TEAEs leading to permanent discontinuation of each study intervention by study intervention will also be provided in a table.

15.2 Deaths, Other Serious Adverse Events, and Other Significant Adverse Events

15.2.1 Deaths

A listing of deaths, if any, will be provided.

15.2.2 Serious Adverse Events

A listing of SAEs, if any, will be provided.

Summary table of the number and percentage of participants with at least one SAE by SOC and PT will also be provided.

15.2.3 Other Significant Adverse Events

The following AESI were defined:

- Infections (serious, severe, and opportunistic, \geq Grade 3)
- Seizures
- Elevated lipase, elevated amylase, pancreatitis
- Liver-related events

More information can be found in the CSP, Section 8.3.7.

AESI will be flagged based on an external excel file and later identified in the AE listings according to these flags. Summary table of the number and percentage of participants with at least one AESI by SOC and PT will also be provided.

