8.2.4 Clinical Safety Laboratory Assessments

- Blood and urine samples will be collected for the clinical laboratory tests listed in [Appendix 5](#) at the time points listed in the Schedule of Assessments. All samples will be clearly identified.
- Additional tests may be performed at any time during the study, as determined necessary by the Investigator or required by local regulations.
- The tests will be performed by **PPD** laboratory; the QuantiFERON® Test will be performed by **PPD**
- The Investigator will review each laboratory report, document this review, and record any clinically significant changes occurring during the study as an AE, unless it does **not** meet the AE definition, as specified in [Appendix 4](#). The laboratory reports will be filed with the source documents.

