Asymptomatic elevations in amylase or lipase or both in participants treated with evobrutinib have been observed at a variety of time points and reported as TEAEs or noted as laboratory abnormalities. In RMS Study MS200527_0086, the incidence of TEAEs of lipase increased was slightly higher in evobrutinib 75 mg once daily and 75 mg twice daily arms (5 [9.4%] and 5 [9.3%], respectively) when compared to other arms (approximately between 4% to 6%). However, shifts from Baseline to highest grade on treatment were similar across all treatment arms for both amylase and lipase. In evobrutinib studies in other indications and in healthy participants, the incidence of TEAEs of increased amylase or lipase, or both was infrequent and

no clinically meaningful differences were observed across treatment arms. Any elevation of $> 2 \times$ ULN of lipase or amylase and any type of pancreatitis are classified as AESIs.

- Liver related events

The elevations of transaminases observed in participants treated with evobrutinib were frequent, asymptomatic, and reversible on discontinuation of evobrutinib. The mechanism is unknown.

Evobrutinib liver AESIs will include transaminases ($> 3 \times$ ULN), bilirubin elevations ($> 1.5 \times$ ULN), biological Hy's Law cases based on laboratory data, any type of acute or chronic hepatitis (any grade), suspected drug-induced liver injury, acute or chronic hepatic failure, fibrosis, cirrhosis, and other liver damage-related conditions.

AESIs have to be reported immediately (within 24 hours). For reporting of AESIs, see [Appendix 4](#).

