
• An AE is any untoward medical occurrence in a patient or clinical study participant, temporally associated with the use of study intervention, whether considered related to the study intervention or not.• An AE can therefore be any unfavorable and unintended sign (including an abnormal laboratory finding), symptom, or disease (new or exacerbated) temporally associated with the use of study intervention. For surgical or diagnostic procedures, the condition/illness leading to such a procedure is considered as the AE rather than the procedure itself.

Events Meeting the AE Definition

• Any abnormal laboratory test results (hematology, clinical chemistry, or urinalysis) or other safety assessments (e.g., ECG, radiological scans, vital signs measurements), including those that worsen from baseline and are judged to be more severe than expected for the participant's condition are considered clinically significant in the medical and scientific judgment of the Investigator (i.e., not related to progression of underlying disease, but may be leading to study intervention discontinuation).• Exacerbation of a chronic or intermittent preexisting condition including either an increase in frequency and/or intensity of the condition.• New conditions detected or diagnosed after study intervention administration even though it may have been present before the start of the study.• Signs, symptoms, or the clinical sequelae of a suspected drug-drug interaction.• Signs, symptoms, or the clinical sequelae of a suspected overdose of either study intervention or a concomitant medication.• “Lack of efficacy” or “failure of expected pharmacological action” per se will not be reported as an AE or a SAE. However, the signs, symptoms, and/or clinical sequelae resulting from lack of efficacy will be reported as an AE or a SAE if they fulfil the definition of an AE or SAE.
--

Events NOT Meeting the AE Definition

• Unless judged by the Investigator to be more severe than expected for the participant's condition, any clinically significant abnormal laboratory findings, other abnormal safety assessments that are associated with the underlying disease, the disease/disorder being studied within the expectedness for participant's condition, as judged by the Investigator.• Medical or surgical procedure (e.g., endoscopy, appendectomy): the condition that leads to the procedure is the AE.

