15.3 Clinical Laboratory Evaluation

Listings and summary statistics at each assessment time will be presented using SI units. Normal ranges will be provided by the laboratory department, and out of range flags will be calculated based on the normal ranges. Laboratory data not transferred from the central laboratory in SI units will be converted to SI units before processing. Both original units and SI units will be provided in the SDTM domain.

Safety laboratory parameters are separated into:

- Hematology (including coagulation)
- Biochemistry
- Urinalysis
- Other tests

Hematology, biochemistry, and coagulation will be summarized by treatment and time point using descriptive statistics for baseline (see definition in Section 9), each evaluation during the study, and change from baseline to each evaluation.

Listings of abnormal test results (low and high) will also be provided.

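### A laboratory value that meets an AESI threshold can be missing from the AESI table, because the SAP counts AESIs only among AE records and does not check them against the laboratory data

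*SAP*

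**What the plan says.** **Definition.** Protocol section 8.3.7 sets laboratory criteria for two of the four AESI groups. For the pancreas, any value above twice the "ULN of lipase or amylase and any type of pancreatitis are classified as AESIs". For the liver, the group includes transaminases above 3 x ULN, bilirubin above 1.5 x ULN and "biological Hy's Law cases based on laboratory data". None of these criteria depends on clinical significance, and every AESI is to be reported within 24 hours. Appendix 4 sends a nonserious AESI to the sponsor on its own report form, by the SAE process.

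**Recording.** Protocol section 8.2.4 tells the Investigator to "record any clinically significant changes occurring during the study as an AE", subject to the AE definition in Appendix 4. The Appendix 4 list of events that meet that definition includes abnormal laboratory results that are "considered clinically significant in the medical and scientific judgment of the Investigator".

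**Analysis.** SAP section 15.2.3 says "AESI will be flagged based on an external excel file and later identified in the AE listings according to these flags". SAP sections 15.1.1 and 15.2.3 summarise AESIs by SOC and PT. Section 15.1 bases the AE analyses on TEAEs unless stated otherwise.

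**Laboratory outputs.** SAP section 15.3 flags values against the laboratory's normal ranges and adds: "Listings of abnormal test results (low and high) will also be provided".

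**The concern.** Three rules about the same laboratory value do not join up. The definition is a fixed number, AE recording involves a judgement, and the analysis sees only what was recorded as an AE. An asymptomatic lipase of 2.5 x ULN meets the AESI definition. If the Investigator considers it not clinically significant and makes no AE entry, there is no record on which the SAP's flag can be placed.

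What is at stake is the AESI count and percentage. Safety of evobrutinib given with the contraceptive is a secondary objective. Section 8.3.7 describes the transaminase elevations seen with evobrutinib as frequent and asymptomatic, which is the kind of finding on which Investigators can differ about clinical significance.

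**Working it through.** There is no figure in the plan to reproduce, because neither document states an expected AESI rate. The check is a comparison of passages, followed by simple arithmetic for scale.

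1. **Can a value be an AESI without judgement?** Yes. The thresholds in 8.3.7 (lipase or amylase > 2 x ULN, transaminases > 3 x ULN, bilirubin > 1.5 x ULN, laboratory Hy's Law) carry no clinical-significance condition.
2. **Must that value become an AE record?** Not stated. Section 8.2.4 and the Appendix 4 list require an entry for clinically significant changes. Neither says that an 8.3.7 threshold settles the question. Appendix 4 requires an AESI form but does not say that the form generates an AE entry.
3. **Can the SAP count it without an AE record?** No. The content of the external file is not described. Whatever it holds, its flags are applied to AE listings, so they can mark only entries that already exist. The SOC and PT layout also presupposes a coded AE term.
4. **Does another SAP output catch it at the AESI threshold?** No. Section 15.3 uses the normal range only. It contains no ULN-multiple table, no Hy's Law derivation, and no reconciliation of laboratory data or AESI forms with AE data. SAP section 9 also keeps repeated and unscheduled measurements out of summaries unless the repeat was made because of unreliable values or technical problems. A high value on an ordinary retest would therefore appear only in a listing.

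**Size per case.** The synopsis sets a maximum of 20 participants. One participant missed, with no other counted AESI, lowers the percentage by 1/n. With n = 20 this is 1/20 = 5 percentage points, and it is larger if fewer are treated. For orientation (the SAP plans no interval here), the two-sided 95% exact upper limit is 1 - 0.025^(1/20) = 16.8% for 0/20 and 24.9% for 1/20.

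**Chance of at least one missed participant.** This needs two quantities that the documents do not give: p, the share of participants who cross a threshold, and c, the share of those who are entered as AEs. With both assumed, the chance is 1 - [1 - p(1 - c)]^20:

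- p = 2%, c = 75%: 1 - 0.995^20 = 9.5%
- p = 5%, c = 50%: 1 - 0.975^20 = 39.7%
- p = 10%, c = 25%: 1 - 0.925^20 = 79.0%

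The range is wide because the inputs are assumed. It shows only that the answer depends on c, which the plan leaves open.

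**The case against.** The strongest reply is that the protocol already requires these values to be reported. Section 8.3.7 and Appendix 4 demand a report within 24 hours whatever the clinical significance. Under the SAE process that AESIs follow, data supplied must agree with the CRF. The general AE definition in Appendix 4 names abnormal laboratory findings without a significance condition. Section 8.2.4 sets a minimum and does not forbid recording other changes. On this view 8.3.7 is the specific rule and prevails.

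Much of this stands. A reader might infer that a threshold value reaches the AE data only if it is judged clinically significant, or that the 24-hour report would be missed. The documents support neither inference: a site that follows 8.3.7 reports the value. What the reply does not supply is the link from the AESI form to an AE record, or any check that the link was made.

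A second reply is that the data are not hidden. Laboratory values are a listed endpoint and AESI incidence is not. Abnormal results are listed, and with at most 20 participants a large excursion would be visible to someone who looks. This also stands. It limits the consequence to the AESI table and does not make that table correct.

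A third is that events may be few. Treatment lasts 14 days. The protocol says that transaminase elevation has not been seen in healthy participants after a single dose or in patients treated for a short time, and that amylase and lipase TEAEs were infrequent in healthy participants. This is fair and bears on priority.

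**Conclusion.** The point holds as a gap between the documents. A value that meets an 8.3.7 threshold but has no AE record would be in the laboratory listings and absent from the AESI table. Each such participant is worth at least 5 percentage points. How often this would occur cannot be estimated from the documents. The conclusion assumes only that the AESI form does not automatically create an AE record, since neither document says that it does.

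Two further inferences should be avoided. The lipase TEAE rates quoted from the RMS study (about 4% to 9.4%) do not measure undercounting. They are events that were recorded as TEAEs, the highest come from the 75 mg arms, and they are not restricted to values above 2 x ULN. Nor can it be said that raised transaminases are the only identified risk of evobrutinib, because another evobrutinib row in the risk table is redacted.

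This is an inexpensive improvement to the safety analysis. It is not a flaw in the primary PK comparison.

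**What to change.** **SAP 15.2.3 and 15.3.** From the laboratory data, derive every value after the first dose, including repeat and unscheduled samples, that meets an 8.3.7 threshold: lipase or amylase > 2 x ULN, transaminases > 3 x ULN, bilirubin > 1.5 x ULN, and Hy's Law by a criterion that the sponsor specifies, since the documents do not define it. Report the number and percentage of participants who meet each threshold in a separate table, because a case without an AE record has no SOC or PT and cannot be placed in the existing one. Before database lock, list these cases against the AE and AESI records and resolve any mismatch.

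**Protocol.** Reconcile section 8.2.4 and Appendix 4 with section 8.3.7, so that it is clear how a value that meets an AESI threshold is recorded and whether the AESI form leads to an AE entry.

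**Cost.** One derivation with its table, one listing and some wording. The analytes are already in the Appendix 5 panel and the laboratory supplies the normal ranges. The AESI count may come out slightly higher.
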